Standard procedures will be employed to see that the delivery of the study therapy and the collection of study data are separated. The Evaluative Component and Clinical Trial Component will be carried out by a different staff member for each Veteran. After the data collector completes the assessments of the Veteran eligible for randomization, the data collector will enter the information for urn randomization into the computer program, but the study therapist will actually give the software command to conduct the urn randomization and generate group assignment. All outcome evaluations will be conducted by the data collector, and Veterans will be asked not to tell the data collector whether SBIRT was delivered. In summary, the clinical trial is not adversely impacted by the presence of a preceding Evaluative Component.

It also is unlikely that the Evaluative Component will not be interpretable because of the Clinical Trial Component. The 480 Veterans who are not randomized (because they do not have risky alcohol use and/or substance use) will be compared to the 80 substance users randomized to No-Additional-Treatment, using a prospective observational design to determine effects of substance use. Both groups will receive serial assessments that are not likely to impact outcomes.

2. Power Analysis for Analysis of the Effects of Substance Use on Outcomes: The effects of substance abuse on outcomes will be analyzed by random effects regression analyses. The treatment attendance outcome will yield a value for each week (attendance or not) and PTSD severity will be assessed at three time points (baseline, 4 and 12 weeks). In the primary analysis, these repeated-measures outcomes will be regressed on substance use, with covariates included that represent potentially confounding differences between Veterans with and without substance use disorders. The proposed sample of 560 participants receiving No-Additional-Treatment, of whom 80 are substance users, has power  $> .80$  to detect standardized mean differences in linear slopes as small as  $\delta = .25$ , allowing for potential downward bias in effects from nonrandom group assignment (Optimal Design software version 1.77), and partial  $\eta^2$  of  $< .1$ , correcting for non-sphericity (G\*Power 3.1.2, Buchner et al., 1992-2009).

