**d. Feasibility of Randomizing Veterans to Therapy that Begins After the Compensation Exam:**

[name] is the P.I. of an RR&D-funded study in which patients who were presenting for Compensation examinations were randomly assigned to one of two types of counseling focusing on vocational rehabilitation. As of June 2011, 75 patients had been randomly assigned of whom 96% attended at least one scheduled therapy session. This demonstrates the feasibility of the proposed model in which patients are referred to attend therapy after their Compensation examinations and the likelihood that Veterans who complete assessments will attend SBIRT if they are assigned to it.

**4. Balancing the study groups:** Participants will be randomized using an urn randomization procedure in order to increase the likelihood of balanced allocation of participants to the two interventions on variables that may affect outcome. In urn randomization, an algorithm modifies ongoing randomization probabilities based on prior composition of treatment groups, maximizing multivariate equivalence of treatment groups (Stout, Wirtz et al. 1994). Thus, urn randomization offers the benefits of balancing allocation of important prognostic variables in treatment groups, while still retaining other benefits of random assignment. A different urn will be used at each site, thus stratifying by site. The factors in the urn will be those that literature has suggested may be related to outcomes in Veterans with PTSD and alcohol use:

- Self-reported illicit drug use in last 28 days
- Days of self-reported alcohol use in the last 28
- Current enrollment in VA psychiatric or substance abuse treatment (yes/no).
- Gender: Women have a telescoped course of substance abuse with adverse

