**C. Single Patient Flow Chart**

\_\_\_\_\_ Veteran receives mailed letter explaining that a telephone call will be coming and allowing the Veteran to opt-out of receiving it

\_\_\_\_\_ Telephone call inviting participation. The research assistant asks the Veteran questions to determine eligibility. Following a script, the research assistant describes the study to the Veteran and schedules an appointment for informed consent and baseline data collection. Appointments will be scheduled on the day of the Compensation examination or up to two weeks before it.

\_\_\_\_\_ Informed consent

\_\_\_\_\_ Evaluative Component: Data collector conducts assessment. If the Veteran meets the substance use and other criteria for randomization, the data collector contacts Dr.

[name] (or her back-up) with the information [name] needs to conduct the urn randomization.

\_\_\_\_\_ Randomization and Scheduling of Next Appointments: The data collector arranges for the Veteran to telephone [name] in a separate room from the research assistant. The data collector asks the Veteran not to tell him/her about any appointments other than the four week follow-up visit.

[name] tells Veterans randomized to SBIRT about the assignment and explains how to make contact with the study therapist. This will happen by all of the following that the Veteran agrees to and/or are feasible: (1) giving the Veteran the therapist's name and telephone number, (2) giving the therapist the Veteran's name and telephone number, (3) giving the Veteran directions to the therapist's office to schedule an appointment. Therapists will schedule therapy sessions immediately after the Compensation exam if feasible and if not, will offer times in the subsequent two weeks.

Regardless of what condition the Veteran is randomized to, [name] will schedule the Veteran's week 4 follow-up appointment with the data collector using a shared online calendar (but no client identifiers).

- \_\_\_\_\_ Veteran undergoes standard Compensation examination
- \_\_\_\_\_ Substance use patients randomized to SBIRT receive counseling.
- \_\_\_\_\_ Weeks 4 and 12: Data collector administers assessments

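### Two sections name different operators for the urn randomization, and one of them makes the treating therapist the person who generates the assignments

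*Combined protocol and SAP*

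**What the plan says.** Two sections of the combined protocol and SAP describe how a Veteran is randomized.

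- **Justification for Combining Evaluative and Clinical Trial Components in a Single Study.** The starting point is "After the data collector completes the assessments of the Veteran eligible for randomization". At that stage the urn factors are keyed in by the data collector. The draw itself is given to someone else: "the study therapist will actually give the software command to conduct the urn randomization and generate group assignment".
- **C. Single Patient Flow Chart.** The data collector contacts a named staff member, or that person's back-up, "with the information [name] needs to conduct the urn randomization". The Veteran then telephones this person from a separate room. The person "tells Veterans randomized to SBIRT about the assignment and explains how to make contact with the study therapist"; one of the listed routes is "giving the therapist the Veteran's name and telephone number". The same person books the week 4 visit for both arms.

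The paragraph on balancing the study groups (section B, Experimental Participants) says that in urn randomization "an algorithm modifies ongoing randomization probabilities based on prior composition of treatment groups", with a separate urn at each site. It does not say who operates the urn, who can see past assignments, or what the urn parameters are.

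**The concern.** The person who generates an assignment should have no stake in it. The study therapist has one. The therapist delivers SBIRT, which includes offering to take the Veteran to a clinic or to telephone with them (section E, Content: Referral to Treatment). Weeks attending treatment is one of the two primary outcomes (section K).

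If the therapist triggers the draw, two things follow that the flow chart's procedure would prevent. The therapist learns which Veterans are controls, although controls are meant to have no study therapy. The therapist can also influence when a draw is made, and the protocol mentions no log or lock that would show a delayed or repeated command.

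There is a practical problem too. With two written procedures and two sites, each site could comply with a different section, and the trial report could not describe allocation without contradicting one of them.

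**Working it through.** The plan gives no figure on this point to reproduce. The check is a comparison of the two sections, followed by a sizing of how predictable an urn is.

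**1. The two procedures side by side**

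| Step | Justification section | Flow chart |
|---|---|---|
| Urn data | Data collector enters them in the program | Data collector passes them to a named person or back-up |
| Draw | Study therapist | The named person or back-up |
| Veteran told | Not stated | By that person, by telephone |
| Therapist learns of the Veteran | By running the draw | After the draw; the hand-off described covers SBIRT Veterans only |

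The blacked-out name does not create the conflict. The flow chart's operator explains how to reach the therapist and may hand over the Veteran's contact details. Neither step makes sense if operator and therapist are the same person.

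**2. What the therapist would learn and control**

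The data collector must stay unaware of the assignment, so in the justification section the therapist is the only person named who could read the result. The therapist would therefore know every assignment that he or she generates, controls included. Assessment and data entry come before the command. The criteria for randomization (section B.3) require every Veteran who completes the assessments and qualifies to be randomized, apart from two listed exceptions. What remains with the therapist is the timing of the command.

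**3. How predictable the next assignment is**

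From the protocol: 160 Veterans to be randomized, two sites, one urn system per site. An equal split (assumed) gives 160 / 2 = 80 per site. The urn parameters are not given, so they are assumed here: start with *a* balls per arm and add *b* balls for the opposite arm after each draw. Then

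P(next is SBIRT) = (a + b × controls so far) / (2a + b × all so far).

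Example with a = 1, b = 1 and 6 controls among 10 assigned: (1 + 6) / (2 + 10) = 7/12 = 0.58.

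Simulated share of correct guesses over 80 assignments, for an observer who has seen all of the previous ones:

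| a, b | Single urn | Four binary factors, draw from the most imbalanced urn |
|---|---|---|
| 0, 1 | 0.548 | 0.631 |
| 1, 1 | 0.543 | 0.605 |
| 1, 3 | 0.546 | 0.618 |
| 3, 1 | 0.538 | 0.583 |

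Chance is 0.50, or 40 correct of 80. The single urn gives 80 × 0.538 = 43.0 to 80 × 0.548 = 43.8 correct. The four-factor urn gives 80 × 0.583 = 46.6 to 80 × 0.631 = 50.5. The protocol lists four balancing factors besides site; treating each as binary, independent and evenly split is a further assumption. In the four-factor case the observer is also assumed to know the Veteran's factor levels and the contents of the urn used.

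**4. How often order could be chosen**

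Recruitment is planned over three years. With an equal split, 160 / (2 × 3) = 26.7 randomizations per site per year, or one every 52 / 26.7 = 1.9 weeks. Two Veterans waiting together at one site would be uncommon.

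**The case against.** The best defence is that this is a loose sentence in a justification section, while the flow chart is the step-by-step instruction that staff would follow. That is plausible, but nothing in the protocol gives the flow chart precedence, so the conflict stands.

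A reader might go further and infer that the therapist could foresee assignments and steer chosen Veterans into SBIRT. The documents do not support that:

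- There is no prepared list to read. The software draws after the command.
- The therapist has no stated role in recruitment, consent, eligibility or data entry.
- Nothing says that the software displays past assignments. The videotaping section (I) implies more than one therapist, so one person seeing all 80 at a site is not established.
- Changing the order needs several Veterans waiting, which step 4 suggests is uncommon.
- The percentages rest on assumed urn parameters and have not been converted into bias on substance-use days or weeks of attendance.

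A reader might also infer that outcome assessment is compromised. It is not affected: the data collector does not run the draw under either procedure, is to be kept unaware of the arm, and is asked to guess it as a check on the blind (section G). Therapist contact with controls is a possibility that the therapist-run procedure leaves open; no passage provides for it.

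Two further limits apply. The flow chart's operator also learns every assignment and could influence timing. What the text shows is that this person is not the treating therapist; the role is blacked out, so full independence cannot be confirmed.

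**Conclusion.** The contradiction is real and needs correcting. It is a conflict about who operates the urn, and one of the two versions places allocation with the person who delivers the intervention. The consequences that stand are the therapist's knowledge of the control assignments that he or she generates and some control over when the command is given.

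The expected bias is small. It depends on a prediction advantage of about 4 to 5 percentage points for a single urn, or 8 to 13 for a four-factor urn, under assumed parameters and an observer who sees every past assignment. It also needs an opportunity to act on the guess, which the plan largely removes. No sample size, endpoint or analysis in the plan changes. The case for acting is that a better procedure is already written into the same protocol.

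**What to change.** Amend the sentence in the justification section so that the flow chart's operator or back-up, and not the treating therapist, issues the urn command. State in both sections that this person passes only SBIRT assignments to the therapist. Confirm that the operator and the back-up do not deliver SBIRT.

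The cost is one rewritten sentence, a clarifying clause in the flow chart and a matching setting for who may run the software. The operator already exists in the flow chart, so that procedure needs no new role. The report should state which procedure was used at each site.

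Optionally, log each command with a time stamp. Neither section provides for this, so it is a small added procedure, but it would make any delayed or repeated command visible.

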#### **D. Research Design and Methods:**

## A. Design for the Proposed Evaluation and Clinical Trial Components

### Sampling of Patients with Substance Use and/or Risky Drinking:

The sampling frame will be the population of OEF/OIF/OND Veterans being evaluated at the participating sites for PTSD who are not already service-connected for it. We will use systematic sampling procedures to define the sample (Cochran, 1977), and will stratify the sample to ensure equal representation of patients from the Tennessee and Connecticut sites. A sampling interval will be estimated to achieve the recruitment rate, and extra recruiting will be included to account for Veterans who refuse to participate and/or are found to be ineligible after approach. The sampling interval will be adjusted after the first six months based on rates of participation from this phase. If the rate of participants meeting substance use criteria for randomization is below the anticipated rate of 25%, we will initiate a brief pre-screen for substance use prior to enrollment and oversample Veterans who pre-screen positive for substance use. This oversampling will allow for sufficient substance-using Veterans to be enrolled in the randomized clinical trial of SBIRT.

As is indicated in the Figure on the preceding page, all Veterans who screen positive for substance use disorders or risky alcohol use will be enrolled in the Clinical Trial Component. A conservative estimate was made that 160 veterans (25% of the sample) would be randomized to SBIRT or No-Additional-Treatment.

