3. Power Analysis for Clinical Trial Component: This study is powered to determine whether Veterans assigned to SBIRT have greater probability of attending substance abuse treatment than those assigned to No-Additional-Treatment. A sample size of 128 is sufficient to detect a standardized effect size of the difference in linear trends in probability of treatment attendance by week between treatment and control groups of  $\delta = .50$  with power =  $.80$  and  $\alpha = .05$  (Optimal Design software, version 1.77). Only minimal attrition is expected because VA service use data will be available for Veterans who do not attend any follow-up assessments, although the sample size allows for loss of 20% of participants.

At least a moderate effect size on treatment attendance is expected because Veterans who agree to substance abuse treatment can be escorted to substance abuse treatment at the time of SBIRT therapy. As described in detail in the Facilities Section, the VA facilities in West Haven and Nashville have comprehensive substance abuse treatment and dual PTSD-substance abuse treatment available on demand.

Assuming a conservative standardized effect of .50 on probability of daily substance abuse, a sample size of 128 is sufficient and allows for 20% attrition. An effect size of 0.5 is within the range of effects on substance abuse outcomes reported for SBIRT interventions (Kaner, Beyer et al. 2007). The effect of the SBIRT intervention on slopes of substance use is likely to be substantial if Veterans assigned to SBIRT preferentially avail themselves of available substance abuse and/or PTSD treatment at VA. It is noteworthy that studies of behavioral interventions for PTSD and concomitant substance use reported large effect sizes. For example, Brady and colleagues reported pre- to post-treatment effects of 1.26 for substance use severity when Exposure Therapy was provided to people with PTSD and cocaine abuse (Brady, Dansky et al. 2001). Mean differences and SDs were used to compute a pre-post effect size of .94 for days of alcohol use in a behavioral intervention targeting PTSD and alcohol use among Veterans (Donovan, Padin-Rivera et al. 2001).

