#### 4. Feasibility:

a. Feasibility of Identifying People Applying for Service Connection for Compensation Exams: At both VACT and TVHS, the Compensation and Pension Clinic schedules Veterans who apply for Compensation for examinations, making this clinic an efficient place to identify potential study participants. We have established procedures to recruit Veterans presenting for Compensation examinations in our previous studies.

b. Feasibility of Enrolling 480 Veterans in the Evaluative Component:

Tennessee: During 2009, TVHS was the site for 299 initial PTSD Compensation examinations for OEF/OIF Veterans, including 22 women.

VA Connecticut: After obtaining IRB approval, our group reviewed the VA charts and Compensation examination reports of 62 consecutive OEF/OIF Veterans who underwent Compensation examinations at VA Connecticut for the six-month period between 7/1/08 and 12/31/08 to estimate rates of substance use and service use. The fact that 62 OEF/OIF Veterans presenting for new PTSD examinations were examined during a six-month period at VA Connecticut, suggests a rate of 124 per year. According to CPRS, between 5/1/12-8/1/12 there were a total of 376 mental health exams scheduled of which 117 were for people not currently service-connected.

i. A rule-out or definitive diagnosis of alcohol abuse was made in eighteen Veterans and two additional Veterans had a substance abuse diagnosis for a total of 32% with an alcohol and/or substance abuse diagnosis. This likely underestimates the rates of substance use and risky drinking because chart review is an insensitive way to identify Veterans with substance use problems (Hawkins, Kivlahan et al. 2007). Only 3% of claimants had received any substance abuse treatment at VA during the three months before the evaluation and only 47% had received any mental health treatment. Altogether, 61% were diagnosed with PTSD on the Compensation examinations and 39% were not.

These results suggest that there is a high prevalence of substance use among OEF/OIF Veterans applying for PTSD-related Compensation, an unmet need for substance abuse treatment, and a range of PTSD-symptom severities.

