#### J. Data Analysis for Evaluative Component:

1. Sample Analyzed for Evaluative Component: The effects of substance abuse on outcomes will be analyzed in the sample of 560 participants who did not receive SBIRT, 80 of whom report risky alcohol/substance use and 480 who did not.

2. Data Reduction: Substance use disorder, PTSD diagnosis, and treatment attendance measures are being collected from more than one source. It is important to reduce the data prior to subsequent analyses to identify the outcomes that will be used in the analyses. These data reduction approaches are shown below:

a. The presence or absence of an Alcohol Use disorder at the time of the Compensation examination will be determined by the best estimate procedure developed by Spitzer and colleagues for validating DSM diagnoses (Spitzer, 1983). This procedure involves reviewing all available sources of information, which for this measure will include the SCID interview, Compensation examination report, substance use calendar, chart review and ICD-9 diagnoses.

A sensitive definition of alcohol use disorder will be employed, and the Principal Investigator will review all cases for which the Compensation Examination and SCID diagnosis are discordant. The reasons to use a sensitive but possibly less specific definition of alcohol use disorder are that an extensive literature documents that there are few "false positive" reports of alcohol and other substance abuse (Kosten and Rounsaville 1992). In a population of Veterans applying for PTSD-based disability, Veterans drinking substantial amounts of alcohol are likely to meet criteria for either Abuse or Dependence, and people with PTSD are particularly vulnerable to the psychological disruptions caused by drugs of abuse (Back, Brady et al. 2006). The same approach will be taken to arriving at best estimate diagnoses for other substances of abuse. The stability of the results will be determined by substituting alternate definitions of the substance use construct.

Descriptive analyses will be conducted to describe the agreement between the different sources of information. For example, the definition of alcohol-use disorders will be compared between the SCID Diagnoses during the assessment battery and the Compensation examinations. Preliminary descriptive and ROC analyses will be conducted of the accuracy of the Compensation examinations for determining alcohol use disorders with the validating criterion being the best estimate diagnosis.

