Because substance use is not randomly assigned, potentially confounding baseline covariates will be considered in the analyses. Baseline level of the dependent variable, e.g. CAPS-rated PTSD severity, will be included in the analysis as a covariate. Other covariates will be included that have been associated with substance use that also might potentially be associated with the outcomes being studied, i.e. PTSD severity and treatment attendance. The covariates will include gender, education level (years of study), current employment status, depression severity (as assessed by the BDI), response to stressful experiences, and meeting criteria for TBI (as assessed by the baseline questionnaire).

We will also examine the within-subjects relationship between the substance use and PTSD outcomes. We hypothesize that improvements in substance use will correspond with improvements in PTSD as evidenced by a significant positive correlation between the slopes of substance use measures (e.g. abstinence, heavy drinking days) and CAPS scores. We also plan to utilize a Structural Equation Model that has the combined benefits of latent curve, autoregressive, and time-specific lagged effects analyses (Bollen & Curran, 2004). We will

analyze the immediate and lagged effects of substance use on CAPS scores. The same approach will be applied to elucidate the relationship between substance use and treatment attendance. Additionally, we will analyze the nature of the effect of each outcome at the previous time point (time t-1) on the value of the same outcome at the current time point (time t). In this manner, we will determine the unique and combined effects of all influences on PTSD symptoms and treatment attendance.

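### The Evaluative Component's stated power (above .80 at δ = .25) is not reproduced: with 80 users against 480 non-users it is about 54% under the convention that returns the plan's own N = 128

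*Combined protocol and SAP*

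**What the plan says.** Section A, item 2 (Power Analysis for Analysis of the Effects of Substance Use on Outcomes) states: "The proposed sample of 560 participants receiving No-Additional-Treatment, of whom 80 are substance users, has power" above .80 "to detect standardized mean differences in linear slopes as small as" δ = .25, citing Optimal Design 1.77. The sentence adds that this allows for possible downward bias from non-random grouping, and it cites a partial η² criterion from G*Power. It gives no alpha, sidedness, slope reliability, attrition or covariate R².

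Section J.1 confirms the split of the 560: "80 of whom report risky alcohol/substance use and 480 who did not". The 80 are the control half of the 160 to be randomized: "A conservative estimate was made that 160 veterans (25% of the sample) would be randomized".

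Item 3 (Power Analysis for Clinical Trial Component) uses the same software and the same kind of effect: "A sample size of 128 is sufficient to detect a standardized effect size of the difference in linear trends", with δ = .50, power .80 and α = .05.

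Section J.4 plans an adjusted model. For example, the baseline level of the outcome "will be included in the analysis as a covariate".

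**The concern.** With a 1:6 split, precision is governed mainly by the smaller group. A total of 560 sounds large, but with only 80 users it carries much less information than 560 divided evenly. A claim of more than 80% power at δ = .25 therefore needs checking.

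The comparison carries Evaluative Hypothesis 1, that users will have worse PTSD over time and attend fewer weeks of treatment than non-users. If power at the smallest effect the plan says it can detect is near one half, a real difference of that size would be missed almost as often as found. A null result could then be misread as ruling out effects of δ = .25.

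**Working it through.** **Inputs.** Groups of 80 and 480 (item 2; section J.1). δ = .25 as a standardized slope difference, so SD = 1 (item 2). α = .05 is stated only for the trial calculation (item 3) and is assumed here; sidedness is not stated, so both are shown. Power is from the noncentral t distribution unless noted.

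**Step 1: reproduce the plan's trial figure.** With 128 in two equal arms, 64 each, and δ = .50:
- SE = sqrt(1/64 + 1/64) = 0.1768
- expected statistic = .50/0.1768 = 2.83
- two-sided power = .801, as stated; 64 per arm is the smallest size that reaches .80.

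A one-sided test would give .879, so the two-sided convention with no penalty for slope error is the one that fits. Also 128/(1 − .20) = 160, which matches the planned number randomized.

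**Step 2: same convention for the Evaluative comparison.**
- SE = sqrt(1/80 + 1/480) = 0.1208
- expected statistic = .25/0.1208 = 2.07
- two-sided power = .54 (normal approximation: Φ(2.07 − 1.96) = .54)
- δ for 80% power = (1.960 + 0.842) × 0.1208 = .338; noncentral t gives .339.

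The equivalent balanced total is 4 × 80 × 480/560 = 274, about half of 560.

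**Step 3: look for a setting that gives more than .80.** All rows use δ = .25.

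| Setting | Power |
|---|---|
| 80 vs 480, two-sided .05 | .54 |
| 80 vs 480, one-sided .05 (80% at δ ≈ .30) | .66 |
| 80 vs 480, covariate R² = .2 (assumed) | .64 |
| 80 vs 480, covariate R² = .4 (assumed) | .76 |
| 80 vs 480, slope reliability .8 (assumed) | .46 |
| 80 vs 480, slope reliability .6 (assumed) | .36 |
| 102 vs 435 (users 32% of 640, half to SBIRT) | .62 |
| 160 vs 480 (all users counted) | .78 |
| 280 vs 280 | .84 |

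Covariates enter as δ/sqrt(1 − R²) and reliability as δ × sqrt(reliability). Reaching .80 with 80 versus 480 needs R² of about .46 two-sided or .31 one-sided. The 32% row borrows the Connecticut chart-review rate in the Feasibility section, which is not the randomization criterion; it only shows that a higher user share does not close the gap. Of the settings in the table, only the even split exceeds .80.

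**Step 4: the partial η² statement.** At 80/480, δ = .25 corresponds to (80/560)(480/560)(.0625) = .0077, or η² of about .008. The η² figure in the plan is a separate criterion for a much larger effect; it is not challenged here and does not support δ = .25.

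**The case against.** The strongest reply is that the convention is inferred. The N = 128 calculation concerns two randomized arms and weekly attendance; the Evaluative claim concerns a non-randomized, covariate-adjusted comparison that includes CAPS at three time points. Nothing says the two runs shared settings, and without the software inputs an arithmetic slip is not proven. Covariates are part of the planned model, so zero precision gain is not the plan's own assumption; an R² near .46, a multiple correlation of about .675, would restore .80. The sentence also carries its own qualifier about downward bias.

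Part of this stands. The 54% is the value under one convention, not the true power, and the even-split explanation remains a conjecture. The rest does not rescue the claim. No R² is stated. The covariates are chosen partly because they are associated with substance use, and that overlap costs precision, so a net gain cannot be presumed. Bias that shrinks the effect lowers power. Slopes from three CAPS assessments are not fully reliable, which also works against the claim.

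It is also fair to say that the matter is limited: the comparison is observational, and the trial's sample size is unaffected.

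**Conclusion.** The concern holds. With 80 users and 480 non-users, the convention that returns the plan's own N = 128 gives about 54% power at δ = .25, and 80% only at δ of about .34. This assumes two-sided α = .05, fully reliable slopes, no attrition and no precision gain from covariates. One-sided testing gives 66%. No value stated in the plan for the missing inputs brings the figure above .80, so the stated detectable effect is too favourable as documented. Power is adequate for larger differences, and the randomized comparison is not affected.

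**What to change.** In item 2, recompute with the 80/480 allocation and replace the δ = .25 claim with a statement such as: *about 54% power for δ = .25 and 80% power for δ ≈ .34, two-sided α = .05, assuming fully reliable slopes, no attrition and no covariate precision gain*. If the authors rely on other values for sidedness, slope reliability, attrition or covariate R², they should state and justify them and report the resulting power instead. That is the better course if the Optimal Design inputs can be recovered, because full slope reliability is a favourable assumption.

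The change is to protocol wording only. Enrolment, endpoints and analysis stay as they are; the only cost is a less favourable stated detectable effect.
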